Hypothesis: Early administration of insulin glargine will result in a lower incidence of rebound hyperglycemia, defined as blood glucose > 180 mg/dL in the 24 hours after IV insulin infusion discontinuation, when compared to usual care for the treatment of diabetic ketoacidosis?

- 6) What is the prevalence of a hypoglycemic (defined as blood glucose < 70mg/dL) event occurring while on IV insulin therapy or in the 24h hours after IV insulin infusion discontinuation with early insulin glargine administration compared to usual care?

Hypothesis: The occurrence of a hypoglycemic event occurring while on IV insulin therapy or in the 24h hours after IV insulin infusion discontinuation with administration of insulin glargine is comparable to usual care.

- 7) Does early administration of insulin glargine result in a statistically lower mean blood glucose value in the 24 hours and (separately) 48 hours after IV insulin infusion discontinuation?

Hypothesis: Early administration of insulin glargine will result in a lower mean value of blood glucose in the 24 and 48 hours after IV insulin infusion discontinuation.

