### Variable list, sources, and data collection

The variables listed on the below data collection form will be incorporated into a secure REDCap database that research staff will use to enter the data. Patients will be assigned study ID numbers in the REDCap database. The REDCap database will contain identifying information, however, if de-identified data needs to be shared outside of the direct study team, the dataset can be downloaded without identifying variables such as MRN.

Variable Name	Role of Variable	Measurement Scale
Study ID	Unique identifier	Continuous (001 – n)
MRN	Link to EMR	String
Full name	Link to EMR	String
Date of ED presentation	Link to EMR	DMY
Age	Descriptive	Continuous
Race	Descriptive	Categorical, as reported in Epic
Ethnicity	Descriptive	Categorical, as reported in Epic
Sex at birth	Descriptive	Categorical, as reported in Epic
End stage renal disease or hepatic disease	Inclusion/exclusion criteria	Binary
Vasopressor dose to treat hypotension at any point during admission	Inclusion/exclusion criteria	Binary
On insulin pump therapy at baseline (prior to ED)	Inclusion/exclusion criteria	Binary
On combination insulin products (i.e. Novolin® 70/30, Novolog® 70/30, Humalog® 75/25, etc.) at baseline	Inclusion/exclusion criteria	Binary
Presenting pH (prior to intervention)	Inclusion/exclusion criteria	Continuous

Time of first pH	Calculate time to resolution	Continuous
Time of short-acting insulin start	Calculate time to resolution	Continuous
Time of first pH > 7.3	Outcome Calculate time to resolution	Continuous
Presenting blood glucose in mg/dL	Inclusion/exclusion criteria	Continuous
Time of first blood glucose < 250 mg/dL	Outcome Calculate time to resolution	Continuous
Blood glucose > 180 mg/dL in the 24 hours after IV insulin infusion discontinuation	Outcome	Binary
Blood glucose < 70mg/dL $\geq$ 1 time at any point while on IV insulin therapy or in the 24 hours after IV insulin infusion discontinuation	Outcome Prevalence of AE (hypoglycemia)	Binary
Blood glucose < 70mg/dL at any point between glargine start and 24 hours after IV insulin infusion discontinuation (control group only)	Outcome Prevalence of AE that may be contributable to study intervention (hypoglycemia)	Binary
Mean blood glucose in 24 and 48 hours after IV insulin infusion discontinuation	Outcome	Continuous
Presenting anion gap	Inclusion/exclusion criteria	Continuous
Time of first anion gap	Calculate time to resolution	Continuous

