### Statistical analysis plan

The primary outcome and secondary outcomes 1-4 and 7 will follow the same analysis plan to study the difference in the distribution of time to an endpoint. First, the distributions for each of these outcomes will be evaluated to determine if the distribution is normal or non-parametric. If the distribution is normal, that outcome will be analyzed using a two-tailed unpaired t-test. If the distribution is non-parametric, that outcome will be analyzed using a Wilcoxon rank sum test. We expect length of stay data to follow a non-parametric distribution. In secondary outcome 2, the outcome measured is the time at which all of the necessary criteria are hit for the first time simultaneously, which accounts for the transient nature of some of these measures.

Secondary outcomes 5-6 will measure the prevalence of each of these outcomes. Prevalence was chosen over incidence in order to account for multiple instances of rebound hyperglycemia or hypoglycemia occurring within the specified timeframe for each and also the amount of time it takes to clinically reverse these conditions. For both of these outcomes, a two-proportion z test will be run to find the difference in the amount of time each treatment arm cumulatively spent with the specified condition. Finally, for the outcomes relying on certain lab values, we will examine time from IV insulin infusion start to outcome labs in both groups. If there is significant variability between the experimental and SOC arms, we will adjust for this statistically. Group randomization should ensure that variability is

equally distributed between groups, however, there is a chance of bias (e.g., if the experimental group fares better and thus are slower to get nursing checks.)

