### **Strengths and limitations**

One strength of this study includes the 24/7 availability of the CCRC Research Intern and the ED Clinical Pharmacist to assist with patient enrollment. This will allow patients to be enrolled on all shifts. The biggest strength in this study is the potential to provide a data set more than double the size of the previous studies on early basal insulin administration in DKA. This study will also follow the patient throughout their hospital stay and look at potential practice changes to decrease the overall length of stay for patients with DKA. We have worked with all relevant departments (ED, Critical Care, Endocrinology, Pharmacy) to ensure that this research will fit into the current workflow for DKA patients without impeding patient care.

The biggest limitation is that while our sample size is larger than the previous publications on this topic, it is still a small pilot study and effects will be somewhat limited to our local setting and practices. This is also a single-center study and not all Emergency Departments have 24/7 ED Clinical Pharmacists available so these practices may not be easily duplicated. Not all patients who are eligible will agree to be in the study, which may cause participation bias. To avoid research bias, a staff member who will not be involved in consent will set up the randomization scheme, so enrollers will be unaware of the next randomization assignment when they approach patients

Furthermore, since this is a pragmatic study in the real-world setting of a functioning, busy ED, research has limited control over components such as timing of standard of care labs and study intervention. We will report and statistically correct for any large variation in timing of outcome labs, such as post-intervention glucose checks.

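### Rebound hyperglycemia and hypoglycemia are to be tested with a two-proportion z test on pooled time, which has no independent units and does not match the yes/no data collected

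*Combined protocol and SAP*

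**What the plan says.** The Statistical analysis plan treats secondary outcomes 5 (rebound hyperglycemia) and 6 (hypoglycemia) as prevalences. It gives the reason: "Prevalence was chosen over incidence in order to account for multiple instances of rebound hyperglycemia or hypoglycemia occurring within the specified timeframe". It adds that the time needed to reverse each condition should count as well. For both outcomes a "two-proportion z test will be run to find the difference in the amount of time each treatment arm cumulatively spent" in the condition. No time unit, denominator or allowance for correlation within a patient is given.

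The variable list describes different data. The rebound field, "Blood glucose > 180 mg/dL in the 24 hours after IV insulin infusion discontinuation", is on a binary scale. The hypoglycemia field that matches aim 6 is also binary: at least one value below 70 mg/dL during the infusion or in the 24 hours after it. A second binary hypoglycemia field, marked for the control group only, runs from the start of glargine. The list has no durations, episode counts or serial glucose values. The only glucose time on it is "Time of first blood glucose < 250 mg/dL". It does include "Mean blood glucose in 24 and 48 hours after IV insulin infusion discontinuation".

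Under Study aims, both outcomes are defined by a threshold within a window, without duration. The hypothesis for aim 6 is that hypoglycemia during the infusion or "in the 24h hours after IV insulin infusion discontinuation with administration of insulin glargine is comparable to usual care".

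**The concern.** A two-proportion z test takes its standard error from the number of independent yes/no observations. In this trial the independent observations are the patients, 66 per arm. Once time is pooled, the sample size becomes the number of time slices. The analyst can make that number as large as desired by cutting time more finely, while the information stays that of 66 patients per arm. A patient who is above 180 mg/dL in one hour is likely to be above it in the next, so the test understates the variance.

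The planned analysis also cannot be computed from the listed variables. Someone would have to choose a method after data are available: pooled time with some unit, or the yes/no fields. These can give opposite answers. Outcome 6 is the trial's safety comparison, and neither a spurious difference nor a non-significant result from an undefined test would inform it.

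**Working it through.** **The plan's own figure.** The documents give no power or precision figure for outcomes 5 and 6. The only one concerns length of stay (ratio 1.31, coefficient of variation 0.6, 66 per arm). It reproduces: the SD of the log is √ln(1 + 0.6²) = 0.5545, which gives 79.9% power. It has no bearing here.

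**Inputs.** From the documents: 66 per arm and alpha 0.05 (Sample size section), the 24-hour rebound window (Study aims), and event rates and infusion times from the studies in the Background. Assumed, because the documents give no values: time unit, intraclass correlation (ICC), share of time in the condition, episode length, and a two-sided test.

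**Step 1: the p-value depends on the unit.** Take 40% versus 36% of the window above 180 mg/dL, pooled 38%. Then z = 0.04 / √(2 × 0.38 × 0.62 / n), with n units per arm.

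| Unit | n per arm | z | p |
|---|---|---|---|
| 4 hours | 66 × 6 = 396 | 1.16 | 0.25 |
| 1 hour | 66 × 24 = 1,584 | 2.32 | 0.02 |
| 15 minutes | 66 × 96 = 6,336 | 4.64 | 4 × 10⁻⁶ |
| 1 minute | 66 × 1,440 = 95,040 | 17.96 | 4 × 10⁻⁷² |

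The design effect is 1 + (k − 1) × ICC, with k units per patient. For hours it is 2.15 at ICC 0.05 and 12.5 at ICC 0.5. Dividing z = 2.32 by the square root of each turns p = 0.02 into 0.11 and 0.51.

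**Step 2: rebound false-positive rate with no true difference.** This is 2 × [1 − Φ(1.96 / √(design effect))].

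| Unit (k) | ICC 0.05 | 0.1 | 0.3 | 0.5 |
|---|---|---|---|---|
| 4 hours (6) | 8% | 11% | 21% | 30% |
| 1 hour (24) | 18% | 28% | 49% | 58% |
| 15 minutes (96) | 41% | 55% | 72% | 78% |
| 1 minute (1,440) | 82% | 87% | 92% | 94% |

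Beta-binomial simulation at mean fractions of 25%, 40% and 60% agrees within about 1 point. On the same simulated data, a Wilcoxon test on each patient's fraction gives 4% to 6%. A z test on one yes/no per patient, by exact enumeration at rates from 10% to 93.5%, gives 4.6% to 5.1%.

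**Step 3: hypoglycemia.** Episodes are short, so the ICC form is less apt. Assume episodes of 0.5 to 1.5 hours in 10% to 55% of patients, with windows of 40 or 48 hours. If T is a patient's hours in the condition and W the window, the variance inflation in hourly units is Var(T) / [E(T) × (1 − E(T)/W)]. It is 4 times that in quarter-hours and 60 times in minutes.

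- One episode per affected patient, 10% affected: E(T) = 0.1 and Var(T) = 0.1 × (1 + 1/12) − 0.1² = 0.0983. The inflation is about 0.99, so the error is about 5% in hours. At 55% affected it is about 0.54, giving 0.8%.
- A second episode in 40% of those affected (the control arm of the 2015 single-center trial had 7 events in 5 patients): 11% in hours at 10% affected, and 4% at 55%.
- Over both cases, simulation gives 18% to 44% in quarter-hours and 73% to 84% in minutes.

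**Step 4: unequal windows for outcome 6.** The window is infusion time plus 24 hours. Early versus control, the retrospective cohort's times give 13.8 + 24 = 37.8 h versus 17.1 + 24 = 41.1 h. The 2012 trial's times give 42 + 24 = 66 h versus 35 + 24 = 59 h. The window can therefore differ by arm in either direction.

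**The case against.** The strongest reply is that the error may never occur. If the form holds only yes/no values, the only z test it supports is the valid per-patient one. The aims speak of an event, and Interventions and Treatments speaks of incidence, which fits that reading. This makes the harm conditional. It does not remove the contradiction, because the analysis section states outright that repeats and duration are to count. Serial glucose values must be read for the 24- and 48-hour means, so a time analysis could be attempted.

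The minute and quarter-hour rows assume a resolution the documents do not support. That is fair; they show only that the answer has no limit as the unit shrinks. The case rests on hours or coarser, where rebound error is still 8% to 58%.

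For hypoglycemia in hours, the error is nominal or conservative with one episode per patient. The 40% repeat rate comes from one arm. Pooling both arms of that trial (11 events in 9 patients, 22% extra) gives about 3% to 9% by the Step 3 formula, and a different rounding of episode boundaries moves the hourly ranges to about 2% to 6% and 6% to 13%. This stands: in hours the hypoglycemia inflation is small and depends on the model.

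The window contrasts are weak predictors. The 2012 trial described its infusion times as similar and only 41% of its patients had DKA; the other source is a retrospective cohort. They show that the direction is uncertain, no more.

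The control-only hypoglycemia field has a different window from aim 6, so the analysis must name the field it uses.

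Finally, the plan's promise, "We will report and statistically correct for any large variation in timing of outcome labs", concerns when glucose is checked. It does not address correlation within a patient.

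**Conclusion.** The concern holds and should be fixed. As written, the test for outcomes 5 and 6 has no defined sample size and cannot be run from the listed variables. For rebound, any positive within-patient correlation pushes the error above 5%; how far depends on the assumed unit and ICC. For hypoglycemia the inflation is clear only in units finer than an hour, under the assumed episode lengths and repeat rates. The defect is confined to these two secondary outcomes. The ICU length-of-stay analysis is untouched.

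**What to change.** Make the patient the unit and reconcile the analysis section with the variable list.

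**Hypoglycemia.** Compare ever/never per patient, using the binary field whose window matches aim 6, and say so. Report the risk difference with a 95% confidence interval. The half-width is 1.96 × √(2p(1 − p)/66): about 10, 14, 16 and 17 points at rates of 10%, 20%, 33% and 55%. A non-significant test should not be read as showing the arms comparable. Either state a margin in advance or report the interval only. Margins that 66 per arm can rule out with 80% power, (1.96 + 0.84) × √(2p(1 − p)/66), are about 15, 20, 23 and 24 points at those rates. Whether any of these is acceptable is a judgement for the sponsor. Report window length and episodes per patient by arm.

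**Rebound.** Choose one in advance:

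- (a) Ever/never per patient, with the z test and a confidence interval. At the retrospective cohort's 88% control rate, the half-width is about 11 points and the drop detectable with 80% power about 20 points. Power for that cohort's own 88% versus 81% would be only about 20%.
- (b) If time in the condition is what is wanted, one fraction of the observed 24-hour window per patient, from time-stamped glucose values, compared by Wilcoxon rank sum. State the rule for time between checks in advance, and report checks per patient by arm.

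**Cost.** SAP wording. Option (b) and the episode counts also need a time-stamped glucose export. No extra patients or tests are needed. P-values will be less extreme. Ever/never drops the repeats and duration the plan wanted to count, so these become descriptive. Ever/never hypoglycemia also keeps a window that can differ by arm: at an equal, constant hourly risk (assumed), the early arm's rate would shift by about −1 to −3 points with the cohort's infusion times, or +1 to +4 with the 2012 trial's.

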## Study aims

Primary Outcome:

- 1) Does early administration of insulin glargine result in a shorter ICU length of stay when compared to usual care for the treatment of diabetic ketoacidosis?

Hypothesis: Early administration of insulin glargine will result in shorter ICU length of stay when compared to usual care in patients with DKA.

Secondary Outcomes:

- 1) Does early administration of insulin glargine result in a shorter hospital length of stay (defined as time between start of insulin infusion and discharge from hospital) when compared to usual care for the treatment of diabetic ketoacidosis?

Hypothesis: Early administration of insulin glargine will result in shorter hospital length of stay when compared to usual care in patients with DKA.

- 2) Does early administration of insulin glargine result in a faster recovery from DKA (defined as blood glucose < 200 and two of: Anion Gap  $\leq$  12, Serum Bicarbonate  $\geq$  15 mEq/L, or pH > 7.3) when compared to usual care for the treatment of diabetic ketoacidosis?

Hypothesis: Early administration of insulin glargine will result in a faster recovery from DKA (defined as blood glucose <200 and two of: Anion Gap  $\leq$  12, Serum Bicarbonate  $\geq$  15 mEq/L, or pH > 7.3) when compared to usual care for the treatment of diabetic ketoacidosis.

- 3) Does early administration of insulin glargine result in a shorter duration of elevated anion gap (defined as time with anion gap > 12) when compared to usual care for the treatment of diabetic ketoacidosis?

Hypothesis: Early administration of insulin glargine will result in a shorter duration of elevated anion gap (defined as time with anion gap > 12) when compared to usual care for the treatment of diabetic ketoacidosis.

- 4) Does early administration of insulin glargine result in a shorter duration of time on IV insulin infusion when compared to usual care for the treatment of diabetic ketoacidosis?

Hypothesis: Early administration of insulin glargine will result in a shorter duration of time on IV insulin infusion when compared to usual care for the treatment of diabetic ketoacidosis.

- 5) Does early administration of insulin glargine result in a lower prevalence of rebound hyperglycemia, defined as blood glucose > 180 mg/dL in the 24 hours after IV insulin infusion discontinuation, when compared to usual care for the treatment of diabetic ketoacidosis?

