Time of first anion gap < 12	Calculate time to resolution	Continuous
Presenting serum bicarbonate level in mEq/L	Inclusion/exclusion criteria	Continuous
Time of first serum bicarbonate < 15 mEq/L	Calculate time to resolution	Continuous
Presence of ketonuria or ketonemia on presentation	Inclusion/exclusion criteria	Binary
Presenting Beta-Hydroxybutyrate in mmol/L	Inclusion/exclusion criteria	Continuous

Type I or Type II Diabetes	Descriptive	Binary
Prior to admission history of current basal insulin usage	Treatment determination if in intervention arm	Binary
Home Insulin Dose	Treatment determination if in intervention arm	Continuous
Time of IV insulin infusion initiation	Ensure protocol compliance Start of outcome measure	Date/Time
Time of IV insulin infusion discontinuation	Outcome	Date/Time
Time of SC insulin glargine administration	Descriptive Ensure protocol compliance	Date/Time
Exact dose of SC insulin glargine administered	Descriptive Ensure protocol compliance	Date/Time
Weight in kg	Determine insulin glargine dose for study order	Continuous
Date/time of ICU admission	Calculate ICU LOS post-infusion for study outcome	Date/time
Date/time of ICU discharge (defined as time of service switch to progressive care or general medicine)	Calculate ICU LOS post-infusion for outcome	Date/time
Date/time of IV insulin infusion start	Calculate LOS post-infusion for study outcome	Date/time
Date/time of hospital discharge	Calculate LOS for study outcome	Date/time

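### The lab-timing safeguard compares and adjusts for time from infusion start to outcome labs, which read literally is outcome 2 itself, nearly outcome 3, and includes infusion duration for the post-infusion glucose outcomes

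*Combined protocol and SAP*

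**What the plan says.** The safeguard is at the end of the Statistical analysis plan. For outcomes that rely on lab values, "we will examine time from IV insulin infusion start to outcome labs in both groups". It continues: "If there is significant variability between the experimental and SOC arms, we will adjust for this statistically". The reason given is a possible bias, for example "if the experimental group fares better and thus are slower to get nursing checks". Strengths and limitations repeats the commitment: "We will report and statistically correct for any large variation in timing of outcome labs, such as post-intervention glucose checks". Neither section defines outcome labs, the model, or how large a difference triggers the step.

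Three other parts of the document determine what the named time is:

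- **Outcome 2 (recovery).** The Statistical analysis plan says "the outcome measured is the time at which all of the necessary criteria are hit for the first time simultaneously". The variable list gives infusion initiation the roles "Ensure protocol compliance Start of outcome measure".
- **Outcome 3 (anion gap).** Study aims defines it as the time the gap is above 12, with no stated start. The variable list collects the time of the first anion gap and of the first one below 12.
- **Outcomes 4 to 7.** Outcome 4 hypothesizes a "shorter duration of time on IV insulin infusion when compared to usual care". Outcomes 5 and 7 use windows that open when the infusion stops (24 h; 24 h and 48 h). Outcome 6 covers the infusion and the following 24 h.

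**The concern.** The worry behind the safeguard is sound. If one arm is checked less often, first-crossing times are recorded late and outcomes based on any reading above or below a limit are missed more often. The quantity chosen to detect this, however, is elapsed time from infusion start. A treatment that speeds recovery or shortens the infusion changes that time even when both arms are sampled identically.

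Two errors follow. The rule can be triggered by a real effect and then condition on that effect. It can also miss a real difference in sampling frequency, because frequency is not what it measures. At stake are the lab-based secondary outcomes 2, 3 and 5-7.

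**Working it through.** **1. The plan's own figure.** The only power figure (Sample size section) is 80% power for a length-of-stay ratio of 1.31, with 66 per arm, CV 0.6 and alpha 0.05. Log-scale SD = sqrt(ln(1 + 0.6²)) = 0.5545. SE = 0.5545 × sqrt(2/66) = 0.0965. ln(1.31)/SE = 0.2700/0.0965 = 2.80. Power = Φ(2.80 − 1.96) = 79.9% (79.3% by noncentral t). It reproduces. The ratio and CV are used below only to scale an illustration, since the plan gives no such figures for recovery.

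**2. Outcome 2.** Let T be the time from infusion start to the lab set that first meets all criteria. The outcome is T and the named covariate is T. In T = a + b·arm + c·T, least squares gives c = 1 and b = 0 exactly. This is algebra and needs no assumption about the data.

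**3. Outcome 3.** If the gap is timed from infusion start, step 2 applies unchanged. If it is timed from the first anion gap, outcome = T + P, where T now ends at the closing lab and P is the time from the first gap to infusion start. Given T, the arm coefficient is only the arm difference in P, which is settled before glargine is given. Simulated adjusted effect: about 0.00 h, with rejection in 4-6% of trials, that is, nominal alpha.

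**4. Outcomes 5 and 7, and the post-infusion part of 6.** Time from infusion start to a check = infusion duration + delay from stop to check. With the infusion times of the cited retrospective study, the first term alone differs by 17.1 − 13.8 = 3.3 h under identical sampling. Adjustment then conditions on a possible mediator. Simulated effects on post-infusion glucose (mg/dL):

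| Assumed mechanism | Unadjusted | Adjusted for time from start |
|---|---|---|
| Direct effect −15, plus 1 per infusion hour | −19.6 | −14.8 (about 25% removed) |
| No direct effect, 1 per infusion hour | −4.8 | −0.1 (about 97% removed) |
| Direct effect −15, no link to duration | −15.1 | −15.1 (unchanged) |
| Direct effect −15, opposite link | −10.4 | −15.1 (enlarged) |

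Adjusting for the delay from infusion stop to the check left the effect unchanged in all four rows.

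**5. How often identical sampling would trigger the rule.** Assumptions not in the documents: lognormal recovery, control median 17.1 h (borrowed from that study's late-group infusion time), true ratio 1.31, CV 0.6, labs about every 4 h in both arms, infusion stopped 2-6 h after recovery, glucose SD 30 mg/dL, 66 per arm, 1,000 trials per scenario, trigger taken as Wilcoxon p < 0.05 on T. The trigger fired in 75-79% of trials. The unadjusted recovery effect was −4.6 to −4.9 h; adjusted for T it was 0.0 h. Adjusted instead for each patient's lab interval, or for the time to the first follow-up lab, it stayed at −4.6 to −4.9 h.

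**6. Does the rule detect what it is meant to detect?** A first crossing is recorded on average half a lab interval late. If the treated arm's 4 h interval becomes 5 h (25% longer), its recorded times rise by about 2.5 − 2.0 = 0.5 h. In the same simulation the unadjusted effect shrank to −4.2 to −4.3 h, and the trigger fired less often (63-64%), because slower sampling offset the treatment effect. With a working treatment, the rule was less likely to fire when the feared problem was present.

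**7. Is the intended quantity collected?** The variable list has presenting lab times, first threshold-crossing times, yes/no glucose flags and mean glucose. It has no draw interval, no count of checks and no time-stamped post-infusion glucose.

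**The case against.** The strongest reply is that outcome labs is undefined and the evident intent is benign. The nursing-check example and the restatement in Strengths and limitations both point to delay or frequency of checks, and step 5 shows that adjusting for those does no harm. That is right about intent. It does not rescue the text: the sentence names a specific quantity, and the listed variables contain nothing that would measure the intended one.

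Other objections stand and set the limits of the point:

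- The step is conditional and has no stated threshold. At the smaller ratios in the protocol's cited studies (11.6/10.2, 9.1/7.8 and 16.91/13.77 h), with a 15 h control median, the same Wilcoxon trigger fires in roughly a quarter, a third and just over half of trials.
- The planned t, Wilcoxon and two-proportion z tests take no covariate, and nothing says an adjusted result would replace them. Equally, an adjustment method would have to be chosen after arm differences are seen.
- The Control group-specific section says both arms have the same labs, with research interns ensuring completion. That lowers the risk of unequal sampling, although Strengths and limitations concedes limited control over lab timing.

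A reader might infer that the safeguard would erase the treatment effect on every lab-based outcome. The documents do not support that. The exact zero is confined to outcome 2 on the literal reading, and outcome 3 is near zero. For post-infusion glucose the direction and size depend on how infusion duration relates to later glucose, about which the documents give no figures.

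**Conclusion.** The point holds as a mis-specified rule, to be corrected before any between-arm data are examined. On the literal reading, adjustment makes the recovery effect exactly zero (algebra) and the anion gap effect about zero. For outcomes 5 and 7 and the post-infusion part of 6 it is adjustment for a possible mediator; in the scenarios run it removed about 0%, 25% or 97% of the effect, or enlarged it. A working treatment can trigger the step with no sampling difference at all, while the sampling difference that prompted it goes unmeasured. The trigger rates and hour and glucose figures rest on the assumptions listed and are illustrations, not predictions.

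This should be fixed, but it does not threaten the main result. ICU stay, hospital stay and infusion duration are not lab-value outcomes, and it is not certain that the adjustment would be applied.

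**What to change.** In the Statistical analysis plan, with matching wording in Strengths and limitations:

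1. Delete the adjustment for time from infusion start. State that the unadjusted randomized comparison is the main analysis for outcomes 2, 3 and 5-7.
2. Replace the metric with sampling density, reported by arm: intervals between consecutive anion gap, bicarbonate, pH and glucose draws up to recovery; number and spacing of glucose checks during the infusion (outcome 6); and the same counted from infusion stop over 24 h (outcomes 5-7) and 48 h (outcome 7).
3. Optionally, prespecify sensitivity analyses: outcome 2 and 3 times treated as interval-censored between the last non-qualifying and first qualifying lab, and time-weighted mean glucose over both 24 h and 48 h for outcome 7.
4. Add the draw times and time-stamped glucose values to the variable list.

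The cost is a short text change and modest extra abstraction of lab times from the medical record. No extra samples are needed.
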